1.5 Summary of Clinical Studies

1.5.1 Clinical Feasibility (FIH) Study

A First-in-Human clinical study was conducted to assess the initial safety and feasibility of the Cross-Seal™ System GEN 1.0 to facilitate hemostasis in patients undergoing percutaneous transcatheter interventions involving access through the femoral artery using an 8-18Fr introducer sheath. Results are demonstrated as shown in **Table 1**. A total of ten (10) subjects were enrolled at a single site in Asuncion, Paraguay between October 26 and 27, 2015. A total of 10 patients completed the study. As shown in **Table 1**, the patient population consisted of 6 (60%) men and 4 (40%) women with a mean age of 66.0 years (range 56.3 to 80.2 years) and mean BMI of 29.2 kg/m² (range 24.2 to 36.7). The mean estimated diameter of femoral artery lumen at the closure site was 9.0 mm and ranged from 7.1 to 11.0 mm as measured via duplex ultrasound. Size 14Fr introducers were utilized in 2 patients and 18Fr introducers were used in 8 patients. The mean

Cross-Seal™ System procedure time was 4 minutes (range 1-8) and mean TTH was 3 minutes and 5 seconds (range 0-13:00). Total estimated blood loss including the interventional procedure was 97.2 mL (range 50-150). The mean Time-to-Ambulation was 3 hours and 12 minutes (range 1:25-9:12) and mean time-to-hospital-discharge was 18 hours and 17 minutes (range 14:05 to 22:22). Four adverse events occurred in 3 patients; 2 hematomas, 1 vessel spasm, and 1 post obstructive flow in the femoral artery. None of the adverse events were serious or unanticipated. All of the events reported were related to the procedure and not to the device and were resolved without any further action required. 100% of patients met the Cross-Seal™ System success defined as closure of the arteriotomy without the need for any access site related adjunctive surgical or endovascular procedures stemming from hemorrhagic, infectious, or ischemic complications. 100% of the patients met the primary and secondary safety endpoints - none had a major or minor vascular complication directly related to the Cross-Seal™ System as defined by VARC-2 (Valve Academic Research Consortium-2). The results of this feasibility study demonstrated that the Cross-Seal™ System is safe and performed as intended.

Table 1. Summary of First-In-Human Clinical Study of the Cross-Seal™ System (GEN 1.0)

Patient Population	
Gender	6 (60%) men and 4 (40%) women
Age	Mean age = 66.0 years (range 56.3 - 80.2 years)
BMI	Mean BMI = 29.2 (range 24.2 - 36.7)
Diameter of femoral artery lumen	Mean = 9.0 mm (range 7.1 - 11.0 mm)
Procedure	
Introducer size	14 Fr, n = 2 18 Fr, n = 8
Cross-Seal™ System procedure time	Mean = 4 minutes (range 1-8 minutes)
TTH	Mean = 3:05 minutes (range 0 - 13:00)
Total estimated blood loss	Mean = 97.2 mL (range 50-150 mL)
Technical Success	100%
Post-procedure	
Time-to-Ambulation	Mean = 3:12 hours (range 1:25-9:12)
Time-to-Hospital-Discharge	Mean = 18:17 hours (range 14:05 - 22:22)
Adverse Events	N = 3 patients; 2 hematoma, 1 vessel spasm, 1 post obstructive flow

1.5.2 CE Study

The CE study was a prospective, multi-center, and single arm study conducted in OUS countries. The primary endpoint of effectiveness was technical success defined as closure of the arteriotomy without the need for any access-site-related adjunctive surgical or endovascular procedures. The primary endpoint of safety was freedom from major VARC-2 events within 30 days of the procedure. Results are demonstrated as shown in **Table 2**.

A total of twenty-six (26) subjects were enrolled across 5 sites in Australia (1), New Zealand (3), and Taiwan (1), between May 30, 2017 and January 12, 2018. Study results from the total of 26 patients' data were monitored and shown in **Table 2**.

The patient population consisted of 20 (77%) men and 6 (23%) women with a mean age of 76.5 years (range 33 – 91 years) and mean BMI is 25.7 (range 20.7-36.7). The mean estimated diameter of femoral artery lumen at the closure site was 8.3 mm and ranged from 6 mm to 11 mm as measure by ultrasound or CT scan. The introducer sheath utilized in study subjects ranged from 8Fr to 18Fr. An 8Fr introducer sheath was utilized in 1 (3.85%) subject, 9Fr introducer sheath was utilized in 1 (3.85%) subject, 10Fr introducer sheaths were utilized in 3 (11.54%) subjects, 12Fr introducer sheaths were utilized in 5 (19.23%) subjects, 14Fr introducer sheaths were utilized in 7 (26.92%) subjects, 16Fr introducer sheaths were utilized in 3 (11.54%) subjects and 18Fr introducer sheaths were utilized in 6 (23.08%) subjects. The mean TTH was 1 minute and 11 seconds (range 00:01 – 11:54). The mean estimated total blood loss including the interventional procedure was 158 ml (range 5 – 600 ml).

A successful ipsilateral “pre-close” percutaneous technique, defined as closure with the Cross-Seal™ System, was achieved in 100% of the subjects with no major ipsilateral access site vascular complication at 30 days follow-up.

Table 2. Summary of CE Clinical Study of the Cross-Seal™ System (GEN 2.0)

Patient Population	
Gender	20 (77%) men and 6 (23%) women
Age	Mean age = 76.5 years (range 33 - 91 years)
BMI	Mean BMI = 25.7 (range 20.7 - 36.7)

Diameter of femoral artery lumen	Mean = 8.3 mm (range 6.0 - 11.0 mm)	
Procedure		
Introducer size	8 Fr, n = 1 9 Fr, n = 1 10 Fr, n = 3 12 Fr, n = 5	14 Fr, n = 7 16 Fr, n = 3 18 Fr, n = 6
TTH	Mean = 1:11 minutes (range 00:01 - 11:54)	
Total estimated blood loss	Mean = 158 mL (range 5 -600 mL)	
Technical Success*	100%	
Post-procedure		

	Cross-Seal™ System GEN 1.0, FIH Study		Cross-Seal™ System GEN 2.0, CE Study	
Sheath Size	Closure Number	Mean TTH (min)	Closure Number	Mean TTH (min)
8Fr	N/A	N/A	N=1	0.23
9Fr	N/A	N/A	N=1	0.63
10Fr	N/A	N/A	N=3	0.47
12Fr	N/A	N/A	N=5	0.55
14Fr	N=2	2.5	N=7	2.26
16Fr	N/A	N/A	N=3	1.95
18Fr	N=8	3.23	N=6	0.7
	Total (10)	3.08	Total (26)	1.19

2 Study Design, Sample Size and Duration

2.1 Study Design

This is a prospective, multi-center, single arm, clinical study to investigate the safety and efficacy of the Cross-Seal™ System.

The target population is comprised of subjects scheduled for elective percutaneous intervention with introducer sheath sizes of 8-18Fr and planned percutaneous arteriotomy closure. Applicable procedures include Transcatheter Aortic Valve

Replacement (TAVR), Endovascular Aneurysm Repair (EVAR), Thoracic Endovascular Aneurysm Repair (TEVAR) and Balloon Aortic Valvuloplasty (BAV).

2.2 Sample Size

A minimum of 3 sites and up to 25 sites in the US are expected to participate in the study with approximately 100 pivotal subjects enrolled. No more than 15% of the pivotal subjects may be enrolled at a single investigational site.

The first 1-2 subjects enrolled by each investigator will be considered roll-in subjects to allow for physician experience with the investigational device. A maximum of 3 study investigators and 6 roll-in subjects will be permitted at each investigational site.

In total, up to 250 subjects will receive the investigational device as part of the clinical study.

2.3 Study Duration

Study enrollment is expected to occur over a 10 to 12 month period. Imaging and follow-up procedures will continue through 30 days post-procedure. Subjects with an abnormal DUS at 30 days will have a repeat DUS at 60 days post-procedure (all DUS will be analyzed by an independent core laboratory). The total study duration is expected to be approximately 24 months.

Note: Due to the COVID-19 pandemic, some patient follow-up visits have been delayed greater than 6 months or completely missed; therefore, making data collection extremely difficult (e.g., missed DUS assessments) to support some of the secondary endpoints. To evaluate safety, we have added an unscheduled visit and telephone assessment (if needed) to be conducted as soon as possible based on physician and hospital regulatory discretion.

3 Study Objective, Hypothesis, and Endpoints

3.1 Study Objective

The study objective is to demonstrate the safety and efficacy of the investigational device to achieve hemostasis of common femoral artery access site in subjects undergoing percutaneous endovascular procedures utilizing 8-18Fr introducer sheath.

3.2 Study Hypothesis

Safety:

The freedom from major complications at the target limb access site within 30 days post-procedure will be greater than the specified PG.

Efficacy:

Following use of the investigational device, the mean TTH will be less than the specified PG.

3.3 Endpoints

This clinical study will evaluate the primary and secondary endpoints described below.

3.3.1 Primary Endpoints

Primary Safety Endpoint:

- Freedom from major complications of the target limb access site within 30 days post-procedure which includes the following:

Major Complications:

- Vascular injury attributable to the investigational device that requires surgical repair, stent-graft, or balloon angioplasty
- Access site-related bleeding attributable to the investigational device that requires transfusion
- Any new access site-related ipsilateral lower extremity ischemia attributable to the investigational device and documented by patient symptoms, physical exam, and/or decreased or absent blood flow on lower extremity angiogram
- Surgery for access site-related nerve injury attributable to the investigational device
- Permanent (lasting > 30 days) access site-related nerve injury attributable to the investigational device
- Access site infection requiring intravenous antibiotics and/or extended hospitalization

Primary Efficacy Endpoint:

- The mean TTH in the Common Femoral Artery (CFA) of the target limb access site with use of the investigational device.

TTH will be evaluated from time of procedural sheath removal to first observed cessation of CFA bleeding (excluding cutaneous or subcutaneous oozing at access site) in the target limb for subjects not requiring adjunctive intervention.

If a sheathless system is used during the procedure, TTH will be calculated from final introducer sheath removal to first observed cessation of CFA bleeding (excluding cutaneous or subcutaneous oozing at access site) in the target limb for subjects not requiring adjunctive intervention.

Adjunctive Intervention is defined as any use of surgical or endovascular intervention OR firm/occlusive manual pressure needed to achieve access site hemostasis (light/non-occlusive pressure to control cutaneous or subcutaneous oozing at the access site is excluded).

3.3.2 Secondary Endpoints

Secondary Safety Endpoints:

- The freedom from minor complications at the target limb access site within 30 days post-procedure which includes the following:

Minor Complications:

- Non-treated pseudoaneurysm attributable to the investigational device and documented by DUS
- Pseudoaneurysm attributable to the investigational device and treated with ultrasound-guided compression, ultrasound-guided thrombin injection, or ultrasound-guided fibrin adhesive injection
- Non-treated or treated arteriovenous (AV) fistula attributable to the investigational device and documented by DUS
- Access site hematoma greater than or equal to 10 cm in diameter, attributable to the investigational device, and confirmed by DUS

- Late (following hospital discharge) access site-related bleeding in target limb
- Lower extremity arterial emboli attributable to the investigational device
- Vein thrombosis attributable to the investigational device
- Transient access site-related nerve injury attributable to the investigational device
- Access site wound dehiscence
- Access site infection treated with intramuscular or oral antibiotics
- Device Related Complications (DRCs) and procedural complications within 30 days post-procedure
- Evaluation of all Adverse Events (AEs) from time of investigational device use within 30 days post-procedure, and through 60 days post-procedure for subject's requiring a repeat DUS, including major and minor complications

Secondary Efficacy Endpoints:

- Technical Success: defined as achievement of hemostasis with the investigational device without the need for any access-site-related adjunctive surgical or endovascular intervention (target limb only).
- Access site closure success: defined as technical success and freedom from major complications within 48 hours of the index procedure or hospital discharge, whichever occurs first (target limb only).
- Treatment Success: defined as technical success and freedom from major complications through 30 days follow-up.
- Subjects requiring adjunctive surgical or endovascular intervention to achieve hemostasis of the access site (target limb only) including type of adjunctive intervention.
- Subjects receiving adjunctive manual compression following use of the investigational device to achieve hemostasis of the access site (target limb only).
 - Type of compression applied (light or firm, where light compression is defined as non-occlusive (i.e., “patent hemostasis”) allowing distal blood flow, and firm compression defined as occlusive prohibiting distal blood flow.
- Time-to-Ambulation: defined as elapsed time from final procedural sheath removal to time when the subject stands and walks at least 20 feet without

re-bleeding.

- Time-to-Discharge (i.e., time of actual discharge defined as the elapsed time between final procedural sheath removal and when the subject is actually discharged from the hospital)
- Occurrence of device failure as defined in Section 13.0

3.3.3 Exploratory Endpoints

- Time-to-Device-Deployment defined as time of guidewire removal during device insertion to time of guidewire reinsertion during device removal, and overall procedure time defined as time of first skin nick/incision to achievement of hemostasis in the access site (target limb only)
- Time-to-Dischargeability (i.e., discharge eligibility defined as the elapsed time between final procedural sheath removal and time when the subject is medically able to be discharged based solely on the assessment of the access site as determined by the investigator.

4 Study Design

This is a prospective, multi-center, single arm, clinical study to investigate the safety and efficacy of the Cross-Seal™ System. The safety and efficacy will be evaluated immediately post-procedure, prior to hospital discharge, through 30 days post-procedure, and through 60 days post-procedure for subjects requiring a repeat DUS.

Study sites will make every attempt to conduct a telephone assessment for patients whose follow-up visits have been affected COVID-19. The assessment will evaluate AEs, concomitant medications and groin health status (which would otherwise be evaluated by a physical exam and DUS).

A subject is considered enrolled into the study if the subject has signed the ICF and meets all eligibility criteria.

4.1 Eligibility Criteria

Inclusion Criteria

1. Subject is \geq 18 years old
2. Subject is scheduled for elective or planned (i.e., not emergent or urgent) percutaneous transcatheter interventional procedures involving access through

the femoral artery using 8-18 Fr introducer sheaths (i.e. BAV, TAVR/TAVI, EVAR, TEVAR)

3. Subject is able to undergo emergent vascular surgery if a complication related to the vascular closure necessitates such surgery
4. Subject is willing and able to complete follow-up requirements
5. Subject has the mental capacity to consent for themselves (i.e., does not require the use of a Legally Authorized Representative), and signs a written Informed Consent Form (ICF) prior participating in the study

Subjects will not be permitted to participate in the study if they meet any of the following general exclusion criteria and/or intra-procedure exclusion criteria:

General Exclusion Criteria

1. Prior intra-aortic balloon pump at access site
2. Subjects with severe inflow disease (iliac artery diameter stenosis > 50%) and/or severe peripheral arterial disease (Rutherford Classification 5 or 6), as confirmed with prior standard of care CT Imaging, duplex ultrasound, and/or intra-procedural fluoroscopy
3. Common femoral artery lumen diameter is < 5 mm
4. In opinion of the investigator, significant scarring of the target access site which would preclude use of the device in accordance with the IFU
5. Prior target artery closure with any closure device < 90 days, or closure with manual compression ≤ 30 days prior to index procedure
6. Prior vascular surgery, vascular graft, or stent in region of access site
7. Subjects receiving glycoprotein IIb/IIIa inhibitors before, during, or after the catheterization procedure
8. Subjects with significant anemia (Hgb < 10 g/dL, Hct < 30%)
9. Subject with known bleeding disorder including thrombocytopenia (platelet count < 100,000), thrombasthenia, hemophilia or Von Willebrand's disease
10. Subject with renal insufficiency (serum creatinine level > 221 μ mol/L or 2.5 mg/dL), on dialysis therapy, or with renal transplant
11. Known severe allergy to contrast reagent that cannot be managed with premedication
12. Inability to tolerate aspirin and/or other anticoagulation/antiplatelet treatment

13. Planned anticoagulation therapy post-procedure such that ACT is expected to be elevated above 350 seconds for more than 24 hours after the procedure
14. Connective tissue disease (e.g., Marfan's Syndrome)
15. Thrombolytics (e.g. t-PA, streptokinase, urokinase), Angiomax (bivalirudin) or other thrombin-specific anticoagulants ≤ 24 hours prior to the procedure
16. Recent (within 8 weeks) cerebrovascular accident or Q-wave myocardial infarction
17. Subjects who are morbidly obese (BMI > 40 kg/m²)
18. Planned major intervention or surgery, including planned endovascular procedure in the target leg, within 30 days following the interventional procedure
19. Subject unable to ambulate at baseline (i.e., confined to wheelchair or bed)
20. Currently participating in a clinical study of an investigational device or drug that has not completed its primary study endpoint
21. Known allergy to any device component
22. Subject is known or suspected to be pregnant or lactating
23. Evidence of active systemic or local groin infection
24. Subject has other medical, social or psychological problem that in the opinion of the investigator precludes them from participating
25. Subject is mentally incompetent or a prisoner
26. New York Heart Association (NYHA) Class IV heart failure that is uncontrolled and requires treatment in the Intensive Care Unit within 24 hours prior to the index procedure
27. Left Ventricular Ejection Fraction (LVEF) < 20%
28. Unilateral or bilateral lower extremity amputation
29. Known existing nerve damage in the target leg
30. Subjects who have already participated in this IDE study

Intra-Procedure Exclusion Criteria

31. Access site above the most inferior border of the inferior epigastric artery (IEA) and/or above the inguinal ligament based upon bony landmarks
32. Access site in the profunda femoris or superficial femoral arteries, or the bifurcation of these vessels
33. Ipsilateral femoral venous sheath during the catheterization procedure
34. Common femoral artery calcium at the arteriotomy site (i.e., target access site), which is visible with prior CT Imaging and/or duplex ultrasound

35. Subject in which there is difficulty inserting the introducer sheath or need for greater than 2 ipsilateral arterial punctures at the start of the catheterization procedure
36. Difficulty in obtaining vascular access resulting in multiple arterial punctures and/or posterior arterial puncture
37. Evidence of a pre-existing hematoma (> 1.5 cm in diameter), arteriovenous fistula, pseudoaneurysm, or intraluminal thrombosis at the access site
38. Marked tortuosity (at the investigator's discretion) of the femoral or external iliac artery in the target leg based on prior CT imaging, fluoroscopy, and/or duplex ultrasound
39. Angiographic evidence of arterial laceration, dissection, or stenosis in the femoral artery that would preclude use of the investigational device
40. Target arteriotomy >18F sheath

The inclusion of subjects using other medications will be left to the discretion of the treating investigator. All such medication use, dose, and schedule will be recorded and documented.

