7.2 Index Procedure

Subjects that meet the general eligibility criteria and have signed the informed consent will have their scheduled interventional procedure (i.e., index procedure) performed in accordance with investigator/investigational site standard practices. Subjects on warfarin or anti-Xa inhibitors must be managed per institutional pre-interventional procedure standard of care.

Prior to the use of the investigational device, the investigator will assess the subject for the intra-procedure eligibility criteria to confirm enrollment in the study. If the subject is enrolled (i.e., signed informed consent and meets all eligibility criteria, including intra-procedural), the investigational device will be utilized for femoral artery closure according to the IFU. Enrolled subjects must also receive anticoagulant and/or antiplatelet medication during the index procedure in accordance with the IFU.

If the subject does not meet all eligibility criteria, the subject cannot be enrolled. The subject will be considered a screening failure and will not have the investigational device utilized. The investigator will perform the femoral artery closure according to their standard practice and the subject will not be followed as part of the study protocol. After completion of the interventional procedure, subjects will be treated in accordance with hospital standard of care and the study protocol.

Note: Only one single access site per subject will be eligible for use of the investigational device and any additional access sites will be managed according to the operator's standard of care. It is recommended the investigational device be used on the primary access site (i.e., ipsilateral) as on the side with the intended larger procedural sheath size. Should the procedure require a sheath that exceeds 18Fr at the primary access site (i.e., does not meet the eligibility criteria), the subject may still be enrolled if the secondary access site (i.e., contralateral to the primary access site) is within the acceptable range of 8-18Fr and meets the eligibility criteria.

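### Exclusion 7 depends partly on drugs received after closure, so, read with the FAS and disposition rules, it could remove a device-treated subject from the primary safety analysis

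*Protocol*

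**What the plan says.** Protocol 4.1, General Exclusion 7, excludes "Subjects receiving glycoprotein IIb/IIIa inhibitors before, during, or after the catheterization procedure". It puts no time limit on receipt after the procedure and does not refer to intention.

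Two other general exclusions also look past the procedure, and both are framed as plans. Exclusion 13 begins "Planned anticoagulation therapy post-procedure such that ACT is expected to be elevated above 350 seconds" and Exclusion 18 begins "Planned major intervention or surgery, including planned endovascular procedure in the target leg".

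On timing, Protocol 4 (Study Design) states: "A subject is considered enrolled into the study if the subject has signed the ICF and meets all eligibility criteria". Protocol 7.2 places the final check before closure: "Prior to the use of the investigational device, the investigator will assess the subject for the intra-procedure eligibility criteria to confirm enrollment in the study". A subject who fails it is a screening failure, does not receive the device, is closed by standard practice, and "the subject will not be followed as part of the study protocol".

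On analysis, the FAS (Protocol 14.2.2.1, SAP 7.2.1) has three conditions: consent, enrollment, and having met the inclusion and exclusion criteria. Protocol 14.2.8 and SAP 7.5 treat a consented subject who does not meet every criterion as a screening failure, leave that subject out of the statistical analyses, and show the subject only in an accountability table. The primary safety endpoint is analyzed on the FAS, or on the safety analysis set built from it (Protocol 14.2.2.6 and 14.2.10.2; SAP 7.2.6 and 7.7.2).

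**The concern.** An eligibility criterion should be answerable when eligibility is decided. Part of Exclusion 7 is answered only by what happens after the device has been used. Its status can therefore change after treatment, and the analysis rules make membership of the primary safety population depend on that status.

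This matters because antiplatelet treatment after closure bears directly on access-site bleeding, and access-site bleeding that needs transfusion is one of the major complications. A subject removed for later drug receipt would take any such event out of the analysis. The study has one arm and tests a proportion against a fixed goal of 85.2%, so there is no comparator in which the same removal could balance out. A few subjects near the boundary can decide the outcome.

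**Working it through.** **1. Can the criterion be decided at the check?**

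| Criterion | Refers to | Knowable before device use? |
|---|---|---|
| Exclusion 7, receipt before or during the procedure | drug already given | yes, up to that moment |
| Exclusion 7, receipt after the procedure | drug given later, no time limit | no |
| Exclusion 13 | planned therapy, expected ACT | yes |
| Exclusion 18 | planned intervention | yes |

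**2. Do the analysis rules reach a treated subject?** The FAS requires that criteria were met, in addition to enrollment. The disposition rule covers consented subjects who do not meet all criteria. Neither is restricted to subjects in whom the device was not used. Later receipt would be on record, because antiplatelet and anticoagulant use is collected through discharge and at follow-up (Protocol 7.5). Taken literally, the rules therefore reach such a subject.

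**3. Would another planned analysis restore the subject?** No. The tipping-point analysis (Protocol 14.2.6, SAP 7.4.2) imputes failures for subjects without a 30-day visit. The other safety sensitivity analyses (Protocol 14.2.10.2.1, SAP 7.7.2) only add or remove roll-in subjects. Secondary endpoints are also summarized on the FAS (Protocol 14.2.10.3, SAP 7.7.3).

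**4. Size.** Inputs from Protocol 14.1.2 and 14.2.10.2: goal 85.2%, assumed event-free rate 94%, and success if the one-sided 95% Clopper-Pearson lower limit exceeds 85.2%. For x event-free subjects of n, the limit is the 5th percentile of a Beta(x, n − x + 1) distribution.

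The plan's own figures reproduce with exact binomial tails:
- n = 78, x ≥ 72: alpha 0.046, power 81.3%
- n = 86, x ≥ 79: alpha 0.049, power 85.6%
- n = 95, x ≥ 87: alpha 0.047, power 88.3%

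The illustration starts one event-free subject short of the threshold and removes one subject who had a major complication (x unchanged, n falls by 1):

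| Before | Lower limit | After | Lower limit | Result changes? |
|---|---|---|---|---|
| 86/95 | 84.05% (fail) | 86/94 | 85.17% (fail) | no |
| 87/96 | 84.21% (fail) | 87/95 | 85.32% (pass) | yes |
| 91/100 | 84.82% (fail) | 91/99 | 85.89% (pass) | yes |

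Starting one short, a single removal changes the result at every n from 96 to 102. At n = 95 it takes two removals (86/93, 86.33%).

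Removing an event-free subject works the other way: 87/95 (85.32%, pass) becomes 86/94 (85.17%, fail).

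The documents give no rate for receipt of these drugs after closure. Assuming 1% to 3% of about 100 pivotal subjects, one to three would be affected, and only those with a major complication would move the result towards a pass.

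**The case against.** **The stronger reading on follow-up.** A reader might infer from the last clause of the 7.2 screening-failure rule that a treated subject who later meets Exclusion 7 also loses protocol follow-up. The documents do not support that. The rule describes a subject found ineligible before closure, in whom the device is not used. Elsewhere the text points to treated subjects being followed:
- Protocol 7.2 keeps a subject in follow-up even when the device fails and bail-out is needed.
- Protocol 7.5.2 asks all subjects to return at 30 days.
- Protocol 8.3 requires adverse events from enrollment onward to be reported and followed.
- Protocol 5.8 does not list later ineligibility among the reasons for ending participation.

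The plan is only silent on a treated subject later found to meet an exclusion. It does not order the loss of follow-up.

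**The case for leaving the text alone.** Exclusion 7 sits in a list applied before participation, so an investigator may read its last part as intended use. The disposition rule speaks of subjects who are screened. SAP 4 ties enrollment to the intra-procedural criteria, and no passage provides for reversing enrollment. Deviations are already to be reported and summarized (Protocol 14.2.13, SAP 7.10). The ambiguity would apply equally to any criterion found unmet after treatment.

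Much of this stands: a sensible team would probably keep the subject. It does not settle the point. The protocol refers to plans in Exclusions 13 and 18 and not in Exclusion 7. The FAS lists meeting the criteria as a condition separate from being enrolled. Nothing says that a criterion met after closure is a deviation only. Exclusion 7 is also the case where the later finding is itself a post-treatment event, so leaving it to judgment once outcomes are known is undesirable in an open single-arm study.

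**Conclusion.** The point holds as one of wording that reaches the primary safety population. Exclusion 7 cannot be fully decided when enrollment is confirmed, and a literal application of the FAS and disposition rules could remove a device-treated subject because of something that happened after treatment.

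The size is conditional. The result moves in the device's favor only if the removed subject had a major complication and the trial lies close to the 85.2% boundary; even then it depends on n. A general claim of bias towards success would go too far, since removing an event-free subject slightly lowers the limit. The number of subjects affected is an assumption throughout. The change is worth making because it is cheap and closes off a discretionary exclusion, not because a large effect has been shown.

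**What to change.** Reconcile Protocol 4, 4.1, 7.2, 14.2.2.1 and 14.2.8 with SAP 4, 7.2.1 and 7.5, and state three things:

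1. Eligibility is fixed at the pre-device check in 7.2.
2. Every subject in whom the device was used stays in the FAS (or, for roll-in subjects, FAS_RI) and in any safety analysis drawn from it, and is followed to 30 days. The screening-failure rule in 14.2.8 and SAP 7.5 applies only to subjects in whom the device was not used.
3. A criterion met or discovered after device use is recorded as a protocol deviation and not as a screening failure.

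The sponsor should also make Exclusion 7 decidable at that check. Which drug exposure should exclude a subject is the sponsor's clinical decision and is not judged here.

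The cost is a few lines in each document. No new data are needed, because antiplatelet and anticoagulant use after the procedure is already collected.
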